9.2.1. Serious Adverse Events

An SAE is any AE from this study that results in one of the following outcomes:

- death
- initial or prolonged inpatient hospitalization
- a life-threatening experience (that is, immediate risk of dying)
- persistent or significant disability/incapacity
- congenital anomaly/birth defect
- important medical events that may not be immediately life-threatening or result in death or hospitalization but may jeopardize the patient or may require intervention to prevent one of the other outcomes listed in the definition above. Examples of such medical events include allergic bronchospasm requiring intensive treatment in an emergency room or at home, blood dyscrasias or convulsions that do not result in inpatient hospitalization, or the development of drug dependency or drug abuse.

All AEs occurring after signing the ICF are recorded in the eCRF and assessed for serious criteria. The SAE reporting to the sponsor begins after the patient has signed the ICF and has received investigational product. However, if an SAE occurs after signing the ICF, but prior to receiving investigational product, the SAE should be reported to the sponsor as per SAE-reporting requirements and timelines (see Section 9.2) if it is considered reasonably possibly related to study procedure.

Study site personnel must alert Lilly or its designee of any SAE within 24 hours of investigator awareness of the event via a sponsor-approved method. If alerts are issued via telephone, they

are to be immediately followed with official notification on study-specific SAE forms. This 24-hour notification requirement refers to the initial SAE information and all follow-up SAE information. Patients with a serious hepatic AE should have additional data collected using the eCRF.

Pregnancy (during maternal or paternal exposure to investigational product) does not meet the definition of an AE. However, to fulfill regulatory requirements, any pregnancy should be reported following the SAE process to collect data on the outcome for both mother and fetus.

Investigators are not obligated to actively seek AEs or SAEs in patients once they have discontinued and/or completed the study (the patient disposition CRF has been completed). However, if the investigator learns of any SAE, including a death, at any time after a patient has been discharged from the study and he/she considers the event reasonably possibly related to the study treatment or study participation, the investigator must promptly notify Lilly.

9.2.1.1. Suspected Unexpected Serious Adverse Reactions

Suspected unexpected serious adverse reactions (SUSARs) are serious events that are not listed in the IB and that the investigator identifies as related to investigational product or procedure. United States 21 CFR 312.32 and European Union Clinical Trial Directive 2001/20/EC and the associated detailed guidances or national regulatory requirements in participating countries require the reporting of SUSARs. Lilly has procedures that will be followed for the identification, recording, and expedited reporting of SUSARs that are consistent with global regulations and the associated detailed guidances.

9.2.2. Adverse Event of Special Interest

9.2.2.1. Hypoglycemia

Patients will collect information on episodes of hypoglycemia starting from Visit 3 until the last study visit (Follow-up Visit or ET Visit). For that purpose, patients will be trained about signs and symptoms of hypoglycemia, how to treat hypoglycemia, and how to collect appropriate information for each episode of hypoglycemia in the study according to the Schedule of Activities (Section 2). Site personnel will enter this information into the eCRF at each visit.

Investigators should use the following definitions and criteria when diagnosing and categorizing an episode considered to be related to hypoglycemia (the plasma glucose [PG] values in this section refer to values determined by a laboratory or International Federation of Clinical Chemistry and Laboratory Medicine plasma-equivalent glucose meters and strips) (ADA 2017, ADA 2018):

Glucose Alert Value (Level 1):

- **Documented symptomatic hypoglycemia** is defined as any time a patient feels that he or she is experiencing symptoms and/or signs associated with hypoglycemia, and has a PG level of ≤ 70 mg/dL (≤ 3.9 mmol/L).
- **Documented asymptomatic hypoglycemia** is defined as any event not accompanied by typical symptoms of hypoglycemia, but with a measured PG ≤ 70 mg/dL (≤ 3.9 mmol/L).

- **Documented unspecified hypoglycemia** is defined as any event with no information about symptoms of hypoglycemia available, but with a measured PG ≤ 70 mg/dL (≤ 3.9 mmol/L).

Clinically Significant Hypoglycemia (Level 2):

- **Documented symptomatic hypoglycemia** is defined as any time a patient feels that he or she is experiencing symptoms and/or signs associated with hypoglycemia, and has a PG level of < 54 mg/dL (< 3.0 mmol/L).
- **Documented asymptomatic hypoglycemia** is defined as any event not accompanied by typical symptoms of hypoglycemia, but with a measured PG < 54 mg/dL (< 3.0 mmol/L).
- **Documented unspecified hypoglycemia** is defined as any event with no information about symptoms of hypoglycemia available, but with a measured PG < 54 mg/dL (< 3.0 mmol/L).

Severe hypoglycemia (Level 3):

- **Severe hypoglycemia** is defined as an episode with severe cognitive impairment requiring the assistance of another person to actively administer carbohydrate, glucagon, or other resuscitative actions. These episodes may be associated with sufficient neuroglycopenia to induce seizure or coma. Blood glucose measurements may not be available during such an event, but neurological recovery attributable to the restoration of BG to normal is considered sufficient evidence that the event was induced by a low BG concentration.

Other hypoglycemia categories:

- **Nocturnal hypoglycemia** is defined as any hypoglycemic event that occurs between bedtime and waking.

If a hypoglycemic event meets the criteria of severe, it needs to be recorded as serious on the AE CRF and reported to Lilly as an SAE.

To avoid duplicate reporting, all consecutive BG values ≤ 70 mg/dL (3.9 mmol/L) occurring within 1-hour period may be considered to be a single hypoglycemic event (Weinberg et al. 2010; Danne et al. 2013).

In each case of suspected or confirmed hypoglycemia, it is important that the event be properly categorized, the effect of the intervention be assessed, and the frequency of hypoglycemia be evaluated. The role of dietary changes and physical exercise (or any other contributing factor) in the development of an event should be established. The patient should receive additional education, if deemed appropriate. Please refer to Section 7.8.2.2 for guidance on management of increased hypoglycemia risks.

9.2.2.2. Severe, Persistent Hyperglycemia

Severe, persistent hyperglycemia will be collected during the trial to assess the risk of extreme imbalance in glycemic control.

Investigators will be trained on the application of criteria for deciding when and how to intervene with patients who do not reach glycemic targets. An additional therapeutic intervention should be considered in patients who develop severe, persistent hyperglycemia after randomization. Rescue medication will be prescribed as an add-on to randomized treatment, and patients will continue to follow the protocol-specified visit schedule as described in Section 7.8.2.3.

9.2.2.3. Pancreatitis

Acute pancreatitis is defined as an AE of interest in all trials with tirzepatide including this trial. Acute pancreatitis is an acute inflammatory process of the pancreas that may also involve peripancreatic tissues and/or remote organ systems (Banks and Freeman 2006). The diagnosis of acute pancreatitis requires 2 of the following 3 features:

- abdominal pain, characteristic of acute pancreatitis (generally located in the epigastrium and radiates to the back in approximately half the cases [Banks and Freeman 2006; Koizumi et al. 2006]; the pain is often associated with nausea and vomiting)
- serum amylase (total and/or pancreatic) and/or lipase $\geq 3X$ ULN
- characteristic findings of acute pancreatitis on computed tomography (CT) scan or magnetic resonance imaging (MRI)

If acute pancreatitis is suspected, appropriate laboratory tests (including levels of pancreatic amylase [p-amylase] and lipase) should be obtained via the central laboratory (and locally, if needed). Imaging studies, such as abdominal CT scan with or without contrast, MRI, or gallbladder ultrasound, should be performed. If laboratory values and/or abdominal imaging support the diagnosis of acute pancreatitis, the patient must discontinue therapy with investigational product(s), but will continue in the study on another glucose-lowering regimen (details on rescue intervention will be provided). The most appropriate diabetes therapeutic regimen will be decided by the investigator, based on the patient's clinical status. A review of the patient's concomitant medications should be conducted to assess any potential causal relationship with pancreatitis.

Each case of an AE of pancreatitis must be reported. If typical signs and/or symptoms of pancreatitis are present and confirmed by laboratory values (lipase or amylase [total and/or pancreatic]) and imaging studies, the event must be reported as an SAE. For a potential case that does not meet all of these criteria, it is up to the investigator to determine the seriousness of the case (AE or SAE) and the relatedness of the event to study drug(s).

Each patient will have measurements of p-amylase and lipase (assessed at the central laboratory) as shown on the Schedule of Activities (Section 2) to assess the effects of the investigational doses of tirzepatide on pancreatic enzyme levels. Serial measures of pancreatic enzymes have limited clinical value for predicting episodes of acute pancreatitis in asymptomatic patients (Nauck et al. 2017; Steinberg et al. 2017a, 2017b). Thus, further diagnostic follow-up of cases of asymptomatic pancreatic hyperenzymemia (lipase and/or p-amylase $\geq 3X$ ULN) is not mandated but may be performed based on the investigator's clinical judgment and assessment of the patient's overall clinical condition. Only cases of pancreatic hyperenzymemia that undergo

additional diagnostic follow-up and/or are accompanied by symptoms suggestive of pancreatitis will be submitted for adjudication.

All suspected cases of acute or chronic pancreatitis will be adjudicated by an independent clinical endpoint committee (CEC). In addition, AEs of severe or serious abdominal pain of unknown etiology will also be submitted to the adjudication committee to assess for possible pancreatitis or other pancreatic disease. Relevant data from patients with acute or chronic pancreatitis and those with severe or serious abdominal pain will be entered into a specifically designed eCRF page by study site or Lilly staff. The adjudication committee representative will enter the results of adjudication in a corresponding eCRF page.

9.2.2.4. Thyroid Malignancies and C-Cell Hyperplasia

Individuals with personal or family history of MTC and/or MEN-2 will be excluded from the study. The assessment of thyroid safety during the study will include reporting of any case of thyroid malignancy including MTC and papillary carcinoma and measurements of calcitonin. This data will be captured in specific eCRFs. The purpose of calcitonin measurements is to assess the potential of tirzepatide to affect thyroid C-cell function, which may indicate development of C-cell hyperplasia and neoplasms.

Tirzepatide should be discontinued (after first confirming the value) if postrandomization calcitonin value is ≥ 35 ng/L and has increased at least 50% over baseline. A consultation with a thyroid specialist (if not available, an endocrinologist) should be obtained. If the increased calcitonin value (≥ 35 ng/L and increases by $\geq 50\%$ compared with baseline) is observed in a patient who has administered a medication that is known to increase serum calcitonin, this medication should be stopped and calcitonin levels should be measured after an appropriate washout period. If the confirmed calcitonin value is < 35 ng/L, tirzepatide should be restarted when it is safe to do so.

9.2.2.5. Major Adverse Cardiovascular Events

Deaths and nonfatal CV AEs will be adjudicated by a committee of physicians external to Lilly with cardiology expertise. The nonfatal CV AEs to be adjudicated include the following:

- myocardial infarction
- hospitalization for unstable angina
- hospitalization for heart failure
- coronary interventions (such as coronary artery bypass graft or percutaneous coronary intervention)
- cerebrovascular events, including cerebrovascular accident (stroke) and transient ischemic attack

9.2.2.6. Supraventricular Arrhythmias and Cardiac Conduction Disorders

Treatment-emergent cardiac conduction disorders will be further evaluated. Patients who develop any event from this group of disorders should undergo an ECG which should be submitted to the central reading center. Additional diagnostic tests to determine exact diagnosis should be performed, as needed. The specific diagnosis will be recorded as an AE. Events that meet criteria for serious conditions as described in Section 9.2.1 must be reported as SAEs.

9.2.2.7. Hypersensitivity Events

All allergic or hypersensitivity reactions will be reported by the investigator as either AEs or, if any serious criterion is met, SAEs. Additional data, such as type of reaction and treatment received, will be collected on any AEs or SAEs that the investigator deems related to study drug(s) via a CRF created for this purpose. Additional samples should also be collected as outlined in Section 9.4.4. Study drug(s) should be temporarily interrupted in any individual suspected of having a severe or serious allergic reaction to the study drug(s). Study drug(s) may be restarted when/if it is safe to do so, in the opinion of the investigator. If study drug(s) is permanently discontinued, the patient will receive another glucose-lowering treatment, judged by the investigator to be appropriate based on the patient's clinical status, and will continue in the trial to collect all planned efficacy and safety measurements.

9.2.2.7.1. *Injection Site Reactions*

Injection site reactions will be collected on the eCRF separate from the hypersensitivity reaction eCRF. At the time of AE occurrence in the tirzepatide group, samples will be collected for measurement of tirzepatide anti-drug bodies (ADAs) and tirzepatide concentration.

9.2.2.7.2. *Anti-Drug Antibodies*

The occurrence of ADA formation will be assessed as outlined in Section 9.4.4.

9.2.2.8. Diabetic Retinopathy Complications

Dilated retinal fundoscopic examination will be performed by a qualified eye care professional (ophthalmologist or optometrist) for all patients between Visit 2 and Visit 3 to exclude patients with proliferative retinopathy and/or maculopathy. The results from this examination will be recorded on a specific retinopathy eCRF as a baseline measure of retinopathy.

A follow-up dilated fundoscopic examination should be performed when clinically indicated by any AE suspected of worsening retinopathy, and the findings should be recorded on the retinopathy eCRF.

9.2.2.9. Hepatobiliary Disorders

All events of TE biliary colic, cholecystitis, or other suspected events related to gallbladder disease should be evaluated and additional diagnostic tests performed, as needed. In cases of elevated liver markers, hepatic monitoring should be initiated as outlined in Section 9.4.5.1 and Appendix 4.

9.2.2.10. Severe Gastrointestinal Adverse Events

Tirzepatide may cause severe GI AEs, such as nausea, vomiting, and diarrhea. Information about severe GI AEs as well as antiemetic/antidiarrheal use will be collected in the eCRF/AE form. For detailed information concerning the management of GI AEs, please refer to Section 7.8.2.5.

9.2.2.11. Acute Renal Events

Renal safety will be assessed based on repeated renal functional assessment as well as assessment of AEs suggestive of acute or worsening of chronic renal failure. Gastrointestinal AEs have been reported with tirzepatide, including nausea, diarrhea, and vomiting. These are

consistent with other GLP-1 receptor agonists (Aroda and Ratner 2011). The events may lead to dehydration, which could cause a deterioration in renal function, including acute renal failure. Patients should be advised to notify investigators in case of severe nausea, frequent vomiting, or symptoms of dehydration.

9.2.2.12. Metabolic Acidosis, Including Diabetic Ketoacidosis

Ketoacidosis, a serious life-threatening condition requiring urgent hospitalization, has been reported rarely in patients with T2DM. Patients who present with signs and symptoms consistent with severe metabolic acidosis should be assessed for ketoacidosis regardless of presenting BG levels, as ketoacidosis may be present even if BG levels are less than 250 mg/dL. Treatment of ketoacidosis may require insulin, fluid, and carbohydrate replacement. Routine bicarbonate assessment will be performed during the course of the study. If lactic acidosis is suspected, metformin should be temporarily discontinued until the resolution of the event.

9.2.2.13. Amputation/Peripheral Revascularization

All cases of amputation and peripheral revascularization should be reported as an AE.

9.2.2.14. Major Depressive Disorder/Suicidal Ideation

The prevalence of depressive symptoms and disorders is increased in patients with T1DM or T2DM (ADA 2017). Any AE of major depressive disorder or suicidal ideation should be reported.

9.2.3. Complaint Handling

Lilly collects product complaints on investigational products and drug delivery systems used in clinical studies in order to ensure the safety of study participants, to monitor quality, and to facilitate process and product improvements.

Patients will be instructed to contact the investigator as soon as possible if he or she has a complaint or problem with the investigational product so that the situation can be assessed.

9.3. Treatment of Overdose

Study drug overdose (more than the specified number of injections) will be reported as an AE. In the event of overdose, refer to the IB for tirzepatide.

9.4. Safety

9.4.1. Electrocardiograms

For each patient, ECGs should be collected according to the Schedule of Activities (Section 2). ECGs should be performed after vital signs are collected and prior to the collection of blood samples for laboratory testing if the patient is not adversely affected by the fasting condition. Patients should be supine for approximately 5 to 10 minutes before ECG collection and remain supine, but awake, during ECG collection. Electrocardiograms should be recorded according to the study-specific recommendations.

Electrocardiograms will initially be interpreted by a qualified physician (the investigator or qualified designee) at the site as soon after the time of ECG collection as possible, and ideally while the patient is still present, for immediate patient management, should any clinically

relevant findings be identified. Any clinically significant findings from ECGs that result in a diagnosis and that occur after the patient receives the first dose of the investigational treatment should be reported to Lilly or its designee as an AE via the eCRF.

All digital ECGs will be obtained using centrally provided ECG machines and will be electronically transmitted to a designated central ECG laboratory. The central ECG laboratory will perform a basic quality control check (for example, demographics and study details) and then store the ECGs in a database. At a future time, the stored ECG data may be overread by a cardiologist at the central ECG laboratory for further evaluation of machine-read measurements or to meet regulatory requirements. The machine-read ECG intervals and heart rate may be used for data analysis and report writing purposes, unless a cardiologist overreading of the ECGs is conducted prior to completion of the final study report (in which case, the overread data would be used).

9.4.2. Vital Signs

Vital sign measurements should be taken before obtaining an ECG tracing and before collection of blood samples for laboratory testing, at visits where required. The participant should sit quietly for 5 minutes before vital sign measurements are taken. For each patient, vital sign measurements should be conducted according to the Schedule of Activities (Section 2) and following the study-specific recommendations.

Any clinically significant findings from vital sign measurements that result in a diagnosis and that occur after the patient receives the first dose of study treatment should be reported to Lilly or its designee as an AE via eCRF.

9.4.3. Laboratory Tests

For each patient, laboratory tests detailed in [Appendix 2](#) should be conducted according to the Schedule of Activities (Section 2).

With the exception of laboratory test results that may unblind the study, Lilly or its designee will provide the investigator with the results of laboratory tests analyzed by a central vendor if a central vendor is used for the clinical trial.

Any clinically significant findings from laboratory tests that result in a diagnosis and that occur after the patient receives the first dose of investigational product should be reported to Lilly or its designee as an AE via eCRF.

9.4.4. Immunogenicity Assessments

Where local regulations and ERBs allow, blood samples for immunogenicity testing will be collected to determine antibody production against tirzepatide as specified in the Schedule of Activities (Section 2).

At the visits and times specified in the Schedule of Activities (Section 2), venous blood samples will be collected to determine antibody production against tirzepatide. To interpret the results of immunogenicity, a PK sample will be collected at the same time points as the immunogenicity sample. All samples for immunogenicity should be taken before dose when applicable and

possible. In the event of drug hypersensitivity reactions (immediate or nonimmediate), additional samples will be collected (including ADA, PK, and exploratory immune safety sample) as close to the onset of the event as possible, at the resolution of the event, and 30 days following the onset of the event. Instructions for the collection and handling of blood samples will be provided by the sponsor. Sample collected at Visit 801 will assess immunogenicity at washout of tirzepatide (5 half-lives post end of treatment).

Treatment-emergent ADAs are defined in Section 10.3.6.

Samples with tirzepatide ADA detected will be titered and evaluated for their ability to neutralize the activity of assigned treatment (tirzepatide-neutralizing antibodies). Samples with tirzepatide ADA detected will also be tested for cross-reactive binding to native GIP and GLP-1, and, if such is detected, then for neutralizing antibodies against native GIP and GLP-1.

Samples will be retained for a maximum of 15 years after the last patient visit or for a shorter period if local regulations and ERBs allow at a facility selected by the sponsor. The duration allows the sponsor to respond to future regulatory requests related to the tirzepatide. Any samples remaining after 15 years will be destroyed.

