- ^t In the event of systemic drug hypersensitivity reactions (immediate or nonimmediate), additional blood samples will be collected including ADA, PK, and exploratory immune safety sample.
- ^u PK samples for immunogenicity must be taken prior to drug administration.
- ^v PK samples will be collected at these visits except for Visit 3 and Visit 14 at time windows of 1 to 24 hours, 24 to 96 hours, OR 120 to 168 hours post dose, as assigned by IWRS. Dependent on the time windows to which a patient gets assigned, they may be required to come to site for PK-specific visits.
- ^w The PK sample after the first dose at Visit 3 should be collected anytime on the same day after administration of the first dose at the site.
- ^x The PK sample after the last dose administered at Week 39 will be collected at Visit 14 (Week 40).
- ^y All PROs should be completed before any other study procedures if the patient is not adversely affected by the fasting condition or completed after the patient has sufficiently recovered from the preceding visit procedures.

3. Introduction

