6.13.6. Immunogenicity

Treatment-emergent anti-drug antibodies (TE ADA) are defined as those with a titer 2-fold (1 dilution) greater than the minimum required dilution (1:10) if no ADAs were detected at baseline (treatment-induced ADA) or those with a 4-fold (2 dilutions) increase in titer compared to baseline if ADAs were detected at baseline (treatment-boosted ADA). A patient is evaluable for TE ADA if the patient has a non-missing baseline ADA result, and at least 1 non-missing postbaseline ADA result.

The frequency and percentage of patients with preexisting ADA, with TE ADA, with cross-reactive antibodies and with neutralizing antibodies will be tabulated by dose, where proportions are relative to the number of patients who are TE ADA evaluable. The frequency and percentage of patients with hypersensitivity and injection site reaction TEAEs by TE ADA status will be tabulated if data warrant.

A listing will be provided of all immunogenicity assessments for those patients who at any time had ADA present. This includes the tirzepatide concentration from a simultaneous PK sample, and the clinical interpretation result.

A listing will be provided for all participant who had ADA present at any time (including baseline) or had any hypersensitivity or injection site reaction TEAE.

Depending on the number of patients with TE ADA, selected efficacy and safety subgroup analyses by TE ADA categories may be performed if deemed necessary.

Treatment-emergent ADA that are associated with AEs of either severe/serious hypersensitivity or severe/serious injection site reaction will be classified as AESIs.

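### ADA samples triggered by a reaction can count towards TE ADA status, which tilts the descriptive table of reactions by TE ADA status towards an association (minor)

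*Protocol*

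**What the plan says.** **Sampling.** Protocol 9.4.4 sets ADA samples at scheduled visits. For a drug hypersensitivity reaction it says that "additional samples will be collected (including ADA, PK, and exploratory immune safety sample) as close to the onset of the event as possible", and then "at the resolution of the event, and 30 days following the onset of the event". Footnote t of the Schedule of Activities (Protocol Section 2) describes the trigger more narrowly: "In the event of systemic drug hypersensitivity reactions (immediate or nonimmediate), additional blood samples will be collected". For an injection site reaction in the tirzepatide group, Protocol 9.2.2.7.1 says that "samples will be collected for measurement of tirzepatide anti-drug bodies (ADAs) and tirzepatide concentration".

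**Status.** SAP 6.13.6 defines TE ADA by titer against baseline, for example "those with a titer 2-fold (1 dilution) greater than the minimum required dilution (1:10) if no ADAs were detected at baseline". On who can be assessed it says: "A patient is evaluable for TE ADA if the patient has a non-missing baseline ADA result, and at least 1 non-missing postbaseline ADA result". Neither sentence separates scheduled from event-driven samples, and Protocol 10.3.6 does not either. SAP 6.13 bases safety analyses on the SS unless stated otherwise, and SAP Table GPGK.6.1 defines the SS as whatever data are available from Study Periods II and III.

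**Use.** SAP 6.13.6 plans that "The frequency and percentage of patients with hypersensitivity and injection site reaction TEAEs by TE ADA status will be tabulated if data warrant". It also plans two listings: all immunogenicity assessments for patients with ADA at any time, and all patients with ADA or with a hypersensitivity or injection site reaction TEAE. TE ADA associated with a severe or serious reaction is classed as an AESI.

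**The concern.** TE ADA status works as an ever-positive flag: one qualifying post-baseline titer is enough, and later negatives do not undo it. An extra sample can therefore only move a patient from negative to positive. Here the extra samples go to patients because they had a reaction, and reactions are then tabulated by the flag. The number of tests depends on the outcome being compared, so the mechanism pushes in one direction.

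TE ADA incidence and hypersensitivity reactions are both named safety endpoints, and this is the planned table that links them. A reader cannot tell a modest real association in it from one produced by the sampling.

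The SAP settles the same question elsewhere. It includes unplanned measurements for the liver enzyme maxima (6.13.2.12.3), the ECG maxima (6.13.4) and the laboratory shift tables (6.13.5), and it excludes them from the laboratory graphs (6.13.5). For ADA, where the extra sampling is tied to the outcome, it gives no rule.

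**Working it through.** The plan states no figure on this point, so there is none to reproduce.

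**Inputs from the documents**
- Scheduled post-baseline ADA samples for a completer: 5 (Visits 4, 6, 12, 14 and 801, read from the immunogenicity row of Table GPGK.1; the column alignment is uncertain in the extracted text).
- Extra samples: up to 3 for a hypersensitivity reaction, at least 1 for an injection site reaction.
- Tirzepatide patients: 3 × 118 = 354.

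**Assumptions (not in the documents)**
- Per-sample probability of a qualifying titer, p: 0.05 to 0.4.
- Within-patient correlation, ρ: 0.2 to 0.8, where 0.8 stands for persistent ADA.
- Reaction rate: 5%.
- No true link between ADA and reactions.

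**Model.** Beta-binomial with s = (1 − ρ)/ρ, a = ps and b = (1 − p)s. The chance of no positive in m samples is the product over i = 0, …, m − 1 of (b + i)/(a + b + i), and P(TE ADA+) is one minus that.

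**Worked case, p = 0.2 and ρ = 0.5** (s = 1, a = 0.2, b = 0.8)
- 5 samples: 0.8 × 1.8/2 × 2.8/3 × 3.8/4 × 4.8/5 = 0.613, so 38.7% are positive.
- 8 samples: 0.613 × 5.8/6 × 6.8/7 × 7.8/8 = 0.561, so 43.9% are positive.
- Spurious odds ratio: (0.439/0.561) / (0.387/0.613) = 1.24.
- Reactions among TE ADA+: 0.05 × 0.439 / (0.05 × 0.439 + 0.95 × 0.387) = 5.6%.
- Reactions among TE ADA−: 0.05 × 0.561 / (0.05 × 0.561 + 0.95 × 0.613) = 4.6%.

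**Range at p = 0.2**

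| ρ | TE ADA+ with 5 / 6 / 8 samples | OR, 1 extra | OR, 3 extra |
|---|---|---|---|
| 0.2 | 53.6% / 57.7% / 63.9% | 1.18 | 1.53 |
| 0.5 | 38.7% / 40.8% / 43.9% | 1.09 | 1.24 |
| 0.8 | 26.9% / 27.6% / 28.7% | 1.04 | 1.09 |

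Over the whole grid the odds ratio is 1.03 to 1.27 for one extra sample and 1.09 to 1.85 for three. The value 1.85 is the corner p = 0.4, ρ = 0.2 (81.5% against 89.1% positive). At ρ = 0.8 the range is 1.03 to 1.04 for one extra sample and 1.09 to 1.10 for three.

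A second calibration fixes TE ADA on scheduled samples at 10%, 30% or 50% and lets ρ run from 0 to 0.9. It gives 1.02 to 1.30 for one extra sample and 1.05 to 2.03 for three. The value 2.03 requires ρ = 0, that is, repeated samples from one patient that are independent of each other.

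**Dilution.** Suppose only some tabled reactors give the three extra samples (p = 0.2, ρ = 0.5). With half of them, P(TE ADA+) among reactors is (0.439 + 0.387)/2 = 0.413 and the odds ratio falls from 1.24 to 1.11. With a quarter it falls to 1.06.

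**Patients and arms** (p = 0.2, ρ = 0.5). There are 354 × 0.05 ≈ 18 reactors, of whom 17.7 × (0.439 − 0.387) ≈ 0.9 are reclassified. An arm's TE ADA incidence shifts by 0.05 × (0.439 − 0.387) = 0.0026, about 0.3 percentage points.

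**With scheduled samples only** and equal scheduled follow-up, both groups have 5 samples and the odds ratio is 1.0 by construction.

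**The case against.** The strongest counter-case has five parts.

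1. The SAP never says that event-driven samples set TE ADA status. The evaluability sentence says who can be assessed, not which samples count. This stands as a limit: counting them is the default reading through the SS, not a written rule.
2. A reader might infer that every tabled reactor gives three extra samples. The documents do not support that. The Schedule footnote limits the trigger to systemic reactions, and SAP 6.13.2.9 tabulates hypersensitivity events that may have no dedicated eCRF. Draws may also coincide with scheduled visits, and a reactor who leaves early loses scheduled samples, which works against the bias. Three is a maximum.
3. The size rests on p and ρ, for which the documents give nothing, and the model treats early and late samples alike. This stands. The direction needs neither value, but the size does.
4. The effect is about one patient in 354 in the worked case. With some 18 reactors, the 95% confidence interval for the odds ratio spans about 2.6-fold either way, in a descriptive table that may not be produced. This stands, and it is why the point is minor.
5. Scheduled-only status would call a patient negative although ADA was found at the reaction. This is a fair objection to replacing the all-samples table, but not to showing both versions.

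The planned listings allow case-by-case judgement, but as described they do not mark which results were event-driven and they do not correct the table.

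**Conclusion.** The point holds as a minor one. Sampling depends on the outcome, no rule keeps the extra samples out of TE ADA status, and the table of reactions by that status is then biased towards an association. With no true link and assumed ADA behaviour, the spurious odds ratio is about 1.03 to 1.10 if ADA persists and up to about 1.85 in an extreme case with three extra samples. It is smaller where not all tabled reactors are sampled, where draws coincide with scheduled visits, or where reactors miss scheduled samples.

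A reader might go further and infer that TE ADA incidence by arm and the AESI classification are compromised too. The documents do not support that. The shift in incidence is negligible (about 0.3 points in the worked case). The AESI rule flags cases for review and compares no groups, and a sample taken at the event is directly relevant to it. No primary or key secondary analysis is affected.

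**What to change.** - **SAP 6.13.6:** present the reactions-by-TE-ADA table twice, side by side: once with TE ADA status from scheduled-visit samples only, once from all samples. State which samples each version uses.
- **Listings:** identify event-driven results in the two listings already planned.
- **Leave unchanged:** keep all samples for TE ADA incidence and for the AESI classification, and keep collecting the event-driven samples.
- **Protocol:** reconcile footnote t of the Schedule of Activities (systemic reactions) with Section 9.4.4 (no such limit) on which reactions trigger extra sampling.

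**Cost.** A sentence or two in the SAP, a visit-type filter, one more version of one table, and a wording change to align the two protocol passages. The downside is that a patient positive only in an event-driven sample appears as TE ADA negative in the scheduled-only version; the adjacent all-samples version and the listings keep that patient visible.
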